5.3 Patient Reported Outcome Administration

NOTE:

NOTE:

5.3.1 PRO Instruments to be Administered

Participants will complete the Health Assessment Questionnaire (HAQ) and the PROMIS Physical Function 20 to assess AIMSS symptoms, the FACT Endocrine Subscale to assess estrogen deprivation symptoms, the FACT-Breast to assess breast cancerspecific concerns, the FACT-General (FACT-G) to assess health-related quality of life, the Assessment of Survivor Concerns (ASC) to assess fear of recurrence, a Treatment Burden scale, and the PROsetta Stone Comorbidity Form and SOAPP study Comorbidity

Rev. 11/13

Rev. 4/14

Rev. 4/14

Rev. 4/14

Rev. 11/13

Rev. Add5

Bother Item. Participants will have a choice between completing these electronically with the NIH Assessment Center or pencil and paper versions of these instruments will be administered to the participants during office visits to their oncologist. It should take approximately 30 minutes for study participants to complete the battery of study instruments.

Rev. Add5

5.3.2 PRO Assessment Schedule

Patients will be assessed according to the following schedule:

- 1.) Baseline*
- 2.) 3 months
- 3.) 6 months
- 4.) 9 months
- 5.) 12 months
- 6.) At the time of symptom onset (if applicable)**
- 7.) At the time the patient discontinues taking anastrozole due to AIMSS***
- 8.) One month after discontinuing anastrozole due to AIMSS

The PRO assessment timepoints correspond to the standard office visits of routine clinic visits to minimize participant burden. However, in the event that a routine clinic visit is not planned or is missed, an attempt should be made to complete the questionnaires on schedule, either by mail or remote electronic entry.

- * The Pain Item on the HAQ will be administered within one week prior to registration. It may be administered orally by staff.
- ** When a study participant has AIMSS symptoms, she should make an appointment to have a MD/provider visit within 2 weeks of onset of symptoms. At this visit it will be determined whether the patient has AIMSS and if it is related to anastrozole. The patient and her MD/provider will decide on a plan to either continue on anastrozole, take a holiday from taking it, or discontinue taking it.
- *** If the patient discontinues taking anastrozole due to AIMSS the MD should follow up within 1 month after discontinuation to have the patient complete an additional PRO assessment. All participants will continue PRO assessments as scheduled up until 12 months, including participants who discontinue anastrozole early for any reason.
- 5.3.3 PRO Administration Instructions Using Paper Forms
 - 5.3.3.1 The questionnaires must be administered at the time points listed above. The patient should be instructed to respond to the questionnaires in terms of her experience during the timeframe specified on each questionnaire.
 - 5.3.3.2 The patient should be asked to read the instructions at the beginning of each questionnaire and complete all the items. It is permissible to assist the patient with the

Rev. 4/14

Rev. 4/14

Rev. 4/14

Rev. 11/13

Rev. 12/14

- completion of the questionnaires as long as the staff person does not influence the patient's responses.
- 5.3.3.3 The questionnaires must be reviewed by the protocol nurse or research coordinator as soon as the patient completes them to ensure all items were marked appropriately. If more than one answer was marked, the patient should be asked to choose the answer which best reflects how she is feeling. If a question was not answered, the patient should be asked if she would like to answer it. The patient should always have the option to refuse. If the patient refuses, it should be indicated on the questionnaire that she declined to answer the item.
- 5.3.3.4 If the patient cannot complete a questionnaire, or if the patient refuses to complete the questionnaire, the reason should be noted according to the instructions in the E1Z11 Forms Completion Guidelines.
- 5.3.4 PRO Administration Instructions Using Assessment Center ™
 - 5.3.4.1 Electronic administration of PRO will be done using the study's website in the PROMIS Assessment Center www.assessmentcenter.net/ac1/Assessments/E1Z11.
 - 5.3.4.2 Prior to accessing the website, each patient will need to be registered by the site. After registering the patient, the site staff member will be provided with a username and password to be given to the patient.
 - 5.3.4.3 Patient-friendly instructions along with additional information about electronic submission of PRO can be found at www.ecog.org/AIMSS QOL.
 - 5.3.4.4 For patients who complete assessments using the Assessment Center, sites will log completion of these assessments in Medidata Rave. If the patient needed assistance or was unable to complete assessments at a given time point, the reason or type of assistance should be provided.

5.3.4.5 For sites with troubleshooting inquiries regarding the use of Assessment Center, the following steps should be followed: 1) All sites should direct troubleshooting inquiries directly to the E1Z11 Data Associate; 2) ECOG will forward unresolved inquiries to Northwestern University research staff; 3) Research staff at Northwestern University may forward unresolved inquiries to Assessment Center for final resolution. NOTE: Assessment Center should not receive any troubleshooting inquiries directly from sites.

5.4 Dose Modifications

See Section 5.1 for criteria for dose interruption, discontinuation, and/or resumption. The daily dose of anastrozole (1mg po daily) cannot be modified when it is taken.

Rev. 12/14

Rev. 4/14

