5.1.1 Treatment

Anastrozole 1 mg, oral, daily for 12 months. Treatment should start within three working days after registration. The patient will be given a pill diary and instructed to complete it and bring it with them to their next MD visit.

5.1.2 Patients should be instructed that when they develop joint pain or stiffness that they should call their MD. Patients should be encouraged to stay on the medication until seen in an office visit.

MD or provider should see the patient within 2 weeks of the patient's call to assess for the likelihood of rheumatologic disease (joints are not red, hot, swollen, or deformed), and determines clinically if the patient has AIMSS, and records his/her impression. The patient completes the questionnaires.

Patient discusses with MD whether to continue or discontinue the drug or start a treatment for AIMSS. A holiday (defined as a drug-free interval of 6 weeks or less) is also an option, as is switching to a different AI, tamoxifen, or participating in a treatment study. The MD will record the recommendation.

- 5.1.3 If and when the patient decides to discontinue anastrozole, the patient will be asked to complete questionnaires. If this was part of a holiday plan, the drug will be considered discontinued if the patient refuses to restart the medication (off the medication for more than 6 weeks).
 - 5.1.3.1 When a patient discontinues the medication, she will be asked for the reasons, and asked to rank them. If pain or other symptoms such as stiffness are the first or second reason, then it will be considered a discontinuation because of AIMSS.
 - 5.1.3.2 The MD will check in with the patient 4-6 weeks later to see if symptoms have resolved, and if anastrozole is discontinued. The patient will complete questionnaires again.

Rev. 11/13

5.1.4 If the patient is to continue anastrozole beyond the 12 months on study, a final questionnaire will be completed at the 12 month time point.

NOTE: All notations of MD above refer to medical protocol (ie, MD, NP or PA); an oncology nurse may also make assessments if felt to be qualified by the Principal Investigator.

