- 6.2.7 PROMIS Physical Function (PF) Short Form 20a - The PROMIS PF 20a consists of 20 items that assess four subdomains of physical function: upper extremity, lower extremity, central, and activity. Responses to the 20 items are summed to create one single score. The PROMIS PF 20 was developed based on items selected from the PROMIS Physical Function 154 item bank. The PROMIS PF 20a contains IRT-based items selected from the PROMIS PF 154 item bank. The "IRT-based" PROMIS PF20 are selected using IRT information content data from over 21,000 subjects to identify the best items and minor qualitative input to ensure that all major areas of Physical Function/Disability were represented in the instrument, with their strongest items. In a study of 451 rheumatoid arthritis patients, the PF20 form was comparable to the HAQ (41). The PF20 form has not been used in patients with AIMSS and will be validated against the HAQ in this study.

Rev. 4/14

NOTE: Please note, Spanish, Korean, Chinese and Japanese versions of the FACT-B form will be available on the ECOG website. Chinese and Spanish version of the HAQ

will be available on the ECOG website. Also, the Spanish version of the PROMIS Physical Function 20-item scale will be posted to the ECOG website.

7. Study Parameters

7.1 Data Collection

Rev. 11/13 Rev. 4/14 Rev.12/14		Baseline ¹	3, 6, 9 and 12 months ^{12,17}	Symptom onset/At diagnosis of AIMSS ^{13,17}	At discontinuation of Anastrozole due to AIMSS ^{12,17}	One month after discontinuation of Anastrozole due to AIMSS ^{14,12,17}	5 Years Post Registration ¹⁶
	Demographics	Х					
	Vital Status	Х					X
	History & Physical Exam, ECOG PS	Х					
	Physical Exam Joints ²	Х	Χ	X	X		
	Routine Blood Tests ³	Х					
	Medication Form ⁴	Х	Χ	X	X	X	
Rev. 4/14	The Stanford Health Assessment Questionnaire (HAQ) and PROMIS Physical Function- Short Form 20a ^{5,6}	X ⁵	Х	Х	×	×	
	Patient-Reported Comorbidity Checklist	Х					
	Provider Completed Comorbidity Form	Х					
Rev. 4/14	FACT-G, FACT-B, and FACT-ES ⁶	Х	Х	Х	Х	Х	
Rev. 4/14	Quality of Life (QOL) Battery including Assessment of Survivor Concerns (ASC), Rakovitch Scale, SOAPP Comorbidity Bother, and SOAP Treatment Burden ⁶	х	Х	Х	X	Х	
1160.4/14	Physician Questionnaire ⁷			Х	Х		
	Recurrence Status ¹⁵	Х	Х	Х	Х		Х
	Pill Calendar ⁸		Χ		Х		
	Biological Sample Submissions ⁹ See Section 10						
	MANDATORY: Blood for Pharmacogenomics (one (1) 10cc yellow top tube) ¹⁰	Х					

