	Blood for Banking for Future Research ¹¹ (serum, [one (1) 10cc red top tube]	Х	Х	Х	Х		

E1Z11

Version Date: April 13, 2023

Rev. 12/14 1. Baseline assessments and questionnaires must be completed by patients after consent is signed and prior to the start of study treatment, unless otherwise noted.

- Rev. 11/13
 2. The baseline physical exam is to include physical exam of the joints and should be done within 4 weeks prior to registration. Providers must document presence of any joint abnormalities (ie, deformity, edema, joint tenderness, effusions) and if any decrease in range of motion at each visit. In follow-up, assessment should include any diagnosis of AIMSS and recommendations on anastrozole dosing.
- Rev. 11/13, 3. This refers to blood tests requested by the provider to assess appropriateness to begin hormonal therapy with anastrozole, if the provider would routinely perform any tests. There are no routine blood tests specifically required by the study.
- Rev. 11/13 4. Include a list of interventions being used by the patient for pain or AIMSS on the Medication Form. MD/provider may allow the patient to complete the medication form as long as they check accuracy after patient completes this form.
- Rev. 11/13 5. Patient's baseline pain rating must be completed within 7 days prior to registration. The response will be recorded on the registration checklist.
- Rev. 11/13, 6. If patients want to use the Assessment Center for completing quality of life assessments, the site should complete the registration prior to asking the patient to complete QOL questionnaires so that their case number can be used as an identifier in Assessment Center. The baseline assessment should be done prior to starting treatment with anastrozole. For subsequent visits, if participant is not able to complete the questionnaires online, paper versions should be given for completion in clinic.
- Rev. 11/13 7. Physician impressions and recommendations regarding AIMSS (stop, continue or holiday) should be recorded on the Physician Questionnaire in Medidata Rave. This can be completed by the physician either electronically or on paper, with information transferred to the electronic CRF by the study staff.
- Rev. 11/13 8. Patient pill calendar/diary should be completed by patient and collected by the site at 3, 6, 9 and 12 month visits and at the time patient discontinues taking anastrozole.

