- Rev. 11/13 9. Kits are being provided for the collection and shipment of the blood samples. Please refer to Section 10.1.2.1 for instructions.
- Rev. 11/13 10. Blood collection for DNA for pharmacogenomics is mandatory as outlined in Section 10. Blood is strongly encouraged to be collected at baseline [after registration, prior to treatment] but may be collected at any other time point if unable to collect at baseline.
- Rev. 11/13 11. Blood (serum) should be collected at baseline (after registration, prior to treatment), at three (3) months **OR** onset of AIMSS (if prior to three [3] months), and at twelve (12) months **OR** discontinuation of anastrozole due to AIMSS. Submit from patients who answer "**Yes**" to "*I agree to provide additional blood for research*."
- Rev. 11/13 12. PRO assessments and clinic visits should be completed every 3 months until 1 year (-/+ 4 weeks) after the initiation of anastrozole therapy. In the event that anastrozole is discontinued due to AIMSS, two additional PRO assessments will be administered: At the discontinuation of Anastrozole due to AIMSS and 1 month after discontinuation of anastrozole due to AIMSS. All participants will complete PRO assessments up until 12 months, including participants who discontinue anastrozole early for any reason.
- Rev. 11/13, 13. Within two weeks after the patient first reports possible AIMSS, there must be an MD assessment/visit to confirm diagnosis and complete PRO's. If the decision is made to discontinue anastrozole due to AIMSS during the same visit as Symptom onset/At diagnosis of AIMSS only one additional MD assessment/visit and repeat PROs must occur one month after discontinuation. If discontinuation due to AIMSS and one month after discontinuation.
- Rev. 4/14 14. If the decision is made to discontinue anastrozole due to AIMSS prior to 12 months, a one month follow-up visit after discontinuation must be completed.
- Rev. 11/13 15. All patients will be followed for recurrence status and survival status until 5 years post study registration. No specific imaging or other assessments are required.

- Rev. 4/14 16. Follow-up visits should be done yearly until 5 years post registration, starting after the patient has completed the 12 months of patient assessments.

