8.1.11 References

AstraZeneca. Arimidex (anastrozole) tablets prescribing information. Wilmington, DE; 2008 Dec.

9. Statistical Considerations

The primary endpoint is defined as discontinuation of treatment following development of AIMSS. A patient will be considered to have developed AIMSS if there is a 20% or greater decline in scores on the HAQ instrument from baseline within one year. At the time of treatment discontinuation, patients and providers will be asked to rank the reasons for treatment discontinuation. If either the patient or the provider lists pain as the first or second-ranked reason and discontinuation is within 3 months of symptom escalation, this will be considered an event. Patients who are lost to follow-up or whose reason for discontinuation is unknown will be considered to be event-free. From previous studies, it is estimated that 40% of patients will develop symptoms, and 25% of patients will discontinue treatment with Als within 1 year due to development of musculoskeletal symptoms.

The enrollment plan is designed to assure adequate enrollment of minority (Asian and African-American) patients. After 600 patients are enrolled from other racial groups, closure of the study to those subgroups will be terminated and accrual will continue among only Asian and African-American patients. When 200 patients are enrolled from the first remaining racial subgroup, closure of accrual to that subgroup will terminate and all remaining patients will be enrolled from the final remaining subgroup. ECOG Minority CCOPs will be strongly encouraged to participate in order to meet targets for minority accrual. While not a separate accrual cohort, ethnicity (Hispanic/non-Hispanic) will also be considered in the analysis plan.

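### The stop-time assessments are scheduled only for stops attributed to AIMSS, while Section 9 and 5.1.3 need reasons from every stop; the provider's ranking has no visible collection point for the rest

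*Combined protocol and SAP*

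**What the plan says.** **Passages covering every stop.** Section 5.1.3 asks a patient who decides to stop anastrozole to complete questionnaires, without restricting the reason. Section 5.1.3.1 adds: "When a patient discontinues the medication, she will be asked for the reasons, and asked to rank them". It then treats the stop as AIMSS-related if pain or a symptom such as stiffness is in her top two reasons. Section 9 also wants the provider's view: "At the time of treatment discontinuation, patients and providers will be asked to rank the reasons for treatment discontinuation". Pain in the top two from either party, with the stop within 3 months of symptom escalation, makes an event. Section 9 also sets a default: patients lost to follow-up, or "whose reason for discontinuation is unknown will be considered to be event-free".

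**Passages covering only stops attributed to AIMSS.** Item 7 of the list in 5.3.2 is "At the time the patient discontinues taking anastrozole due to AIMSS", and item 8 is the assessment one month later, under the same restriction. In Section 7.1 the stop column is headed "At discontinuation of Anastrozole due to AIMSS", and the only other stop column is the one-month follow-up of that visit. Footnote 12 agrees: "In the event that anastrozole is discontinued due to AIMSS, two additional PRO assessments will be administered". Footnotes 13 and 14 are written on the same basis.

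**The provider form.** The calendar marks the "Physician Questionnaire" at symptom onset or AIMSS diagnosis and at the AIMSS stop, nowhere else. Footnote 7 describes its content: "Physician impressions and recommendations regarding AIMSS (stop, continue or holiday) should be recorded on the Physician Questionnaire in Medidata Rave". A ranking of reasons is not mentioned.

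**The concern.** Whether a stop counts as AIMSS is the result of the ranking, yet the visit schedule takes that result as its trigger. The paper-form instructions in 5.3.3.1 make the listed time points mandatory, so site staff have good reason to work from the list. If a patient says she is stopping for hot flashes, a site following 5.3.2 and Section 7.1 finds no stop visit, no provider form and no ranking form to complete. Section 9 would still count her as an event if either she or her provider put pain second and the other conditions were met.

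At stake is how completely primary events are ascertained. A reason that was never recorded becomes a non-event under the Section 9 default, so it lowers the event count without showing up as missing data. The analysis of stops for any reason in Section 9.2 and the model of the decision to stop in objective 2.2.7 would also benefit from stop-time data that the calendar schedules only for AIMSS stops.

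**Working it through.** **Step 1. The passages side by side.**

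| Place | Stops covered | Patient ranking | Provider ranking | Questionnaires at the stop |
|---|---|---|---|---|
| 5.1.3, 5.1.3.1 | any | yes | not mentioned | yes |
| Section 9 | any | yes | yes | visit not named |
| 5.3.2, items 7-8 | AIMSS only | not named | not named | yes |
| 7.1 stop columns, footnotes 12-14 | AIMSS only | no row | Physician Questionnaire, not described as a ranking | yes |

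The patient's ranking and the questionnaires have one passage that covers every stop and others that do not. The provider's ranking is required by Section 9 alone, and the schedule gives it no collection point when the stop is not attributed to AIMSS.

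**Step 2. Reproduce the plan's power figure.** Inputs from Section 9.1: N=1000, one-sided alpha 0.0025 (0.025/10), Cochran-Armitage trend test, Hardy-Weinberg proportions, additive log-odds. With genotype shares g_i, event probabilities p_i, allele count i = 0, 1, 2 and mean count m:

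- U = Σ g_i (i − m) p_i
- s0 = √[p̄(1 − p̄) Σ g_i (i − m)² / N]
- s1 = √[Σ g_i (i − m)² p_i(1 − p_i) / N]
- power = Φ[(U − 2.807 s0)/s1]

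Table 2 gives a detectable odds ratio of 1.55 for 30% discontinuing and minor allele frequency (MAF) 20%. The formula gives power 0.814 at 1.55, and exactly 80% at 1.541. All eight N=1000 entries reproduce to within about 1.5%.

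**Step 3. Base case.** Section 9 expects 25% of patients to stop for musculoskeletal symptoms, or 250 events in 1000. With MAF 20%, g = 0.64, 0.32, 0.04 and m = 0.4. At odds ratio 1.575, p = 0.2148, 0.3011, 0.4043. Then U = 0.0287, s0 = √(0.25 × 0.75 × 0.32/1000) = 0.00775, s1 = 0.00814, and power = Φ[(0.0287 − 0.0217)/0.00814] = 0.80.

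**Step 4. Lose a share f of true events.** The documents give no value for f; 5%, 10% and 20% are assumptions. Loss is taken as independent of genotype, so each p_i is multiplied by (1 − f).

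| f | Events lost of 250 | Observed rate | Power |
|---|---|---|---|
| 0 | 0 | 25% | 80% |
| 5% | 12.5 | 23.75% | 77% |
| 10% | 25 | 22.5% | 73% |
| 20% | 50 | 20% | 65% |

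For f = 20%: U = 0.8 × 0.0287 = 0.0230, s0 = √(0.20 × 0.80 × 0.32/1000) = 0.00716, s1 = 0.00762, and power = Φ[(0.0230 − 0.0201)/0.00762] = 0.65.

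For true rates of 20-30% and MAF 10-40%, starting each time from the odds ratio with 80% power, the result is 72-73% at f = 10% and 63-66% at f = 20%.

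**Step 5. Effect on the odds ratio.** At f = 20%, p becomes 0.1718 and 0.2409 for 0 and 1 minor alleles. The odds ratio is (0.2409/0.7591)/(0.1718/0.8282) = 1.53, against 1.57 before. At f = 10% it is about 1.55.

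**The case against.** A reader might infer that the protocol collects ranked reasons only at AIMSS stops, so that stops with pain as the second reason are lost by design. The documents do not support that. Section 5.1.3.1 puts the steps in a workable order: every stopping patient ranks her reasons, pain in the top two makes the stop AIMSS-related, and the AIMSS column then applies. Nor can it be said that no stop-time HAQ is intended for other stops: 5.1.3 asks for questionnaires at any stop, and 5.1 lists the HAQ among them.

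Other safeguards exist. A patient reporting joint symptoms is to be seen within 2 weeks, and the calendar marks the HAQ, joint examination and Physician Questionnaire for that visit. The HAQ continues at 3, 6, 9 and 12 months after a stop for any reason, which largely protects the HAQ part of the endpoint. Because either party's ranking is enough in Section 9, once the patient's ranking is held a missing provider ranking matters only when the provider alone puts pain in the top two.

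Part of the power loss also lies within planned uncertainty. Table 2 already allows a 20% event rate; with no misclassification, that rate at an odds ratio of 1.57 gives about 73% power.

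All of this stands, and it narrows the point. It does not tell a site which passage governs, and it provides no place for the provider's ranking. The Forms Completion Guidelines, to which Section 11 refers for the forms schedule, are not among the documents and may contain a stop form for any reason.

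**Conclusion.** The point holds as an internal inconsistency in when primary-endpoint data are collected. The clearest gap is the provider's ranking at stops not attributed to AIMSS. For the patient's ranking and the stop-time HAQ, data are at risk only where a site follows 5.3.2 and Section 7.1 in preference to 5.1.3.

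The size is unknown. The fall from 80% to about 77%, 73% or 65% rests entirely on assumed losses of 5%, 10% or 20% of true events, unrelated to genotype, and the safeguards above could make the actual loss smaller. A reader might also infer a seriously diluted odds ratio or a raised false-positive rate. Neither follows: the odds ratio moves only from 1.57 to about 1.53 at a 20% loss, and loss unrelated to genotype leaves equal event rates across genotypes under the null. The cost is power. This is a cheap improvement worth making, not a flaw that undermines the design.

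**What to change.** Reconcile 5.3.2, Section 7.1 and footnote 12 with 5.1.3 and Section 9. Make the data-collection column cover discontinuation of anastrozole for any reason, and place there a ranked-reasons form completed by both patient and provider, together with the HAQ. Keep the assessment one month after stopping for AIMSS stops only. This concerns data collection and leaves treatment decisions untouched.

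The cost is calendar wording plus, for patients who stop for other reasons, one short form and one questionnaire set that 5.1.3 already appears to intend. If the Forms Completion Guidelines already contain an any-reason stop form with both rankings, only the calendar and schedule wording needs aligning.
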